## Appendix 2 Schedule of Pharmacokinetic Samples

Visit	Timepoint	Sample Type
Sparse PK Sampling (all patients) a		
Visit 1 (Day 1)	One sample between 0.5 and 2 hours post-dose	Drug PK (plasma)
Visit 2 (Day 2) b	24 hours post-dose	Drug PK (plasma)
Visit 3 (Day 4) b	72 hours post-dose	Drug PK (plasma)
Visits 4–5 (Days 6–10)	Only one sample is to be collected during the follow-up period; this sample may be collected at follow-up Visit 4 or 5	Drug PK (plasma)
Intensive PK samples c		
Visit 1 (Day 1)	One sample between 0.5 and 2 hours, one sample at 4 hours, and one sample at 6 hours	Drug PK (plasma)
Visit 2 (Day 2) b	24 hours post-dose	Drug PK (plasma)
Visit 3 (Day 4) b	72 hours post-dose	Drug PK (plasma)
Visits 4–5 (Days 6–10)	Only one sample is to be collected during the follow-up period; this sample may be collected at follow-up Visit 4 or 5	Drug PK (plasma)

PK= pharmacokinetic.

- a Samples will be used for S-033447 determination in patients aged  $\geq 2$  years; baloxavir marboxil and S-033447 determination in patients aged  $< 2$  years.
- b Patients will be assigned to have either the Day 2 or the Day 4 sample.
- c Patients undergoing intensive PK assessments are expected to account for 15%–30% of the total patient population and will be distributed approximately equally among age groups. Samples will be used for baloxavir marboxil and S-033447 determination.

### Appendix 3

## Canadian Acute Respiratory Illness and Flu Scale (CARIFS) Questionnaire

Item	No Problem	Minor Problem	Moderate Problem	Major Problem	Don't Know/Not Applicable
1. Poor appetite .....					
2. Not sleeping well					
3. Irritable, cranky, fussy.....					
4. Feels unwell .....					
5. Low energy, tired .....					
6. Not playing well.....					
7. Crying more than usual .....					
8. Needing extra care .....					
9. Clinginess.....					
10. Headache.....					
11. Sore throat.....					
12. Muscle aches or pains .....					
13. Fever .....					
14. Cough.....					
15. Nasal congestion, runny nose.....					
16. Vomiting .....					
17. Not interested in what's going on					
18. Unable to get out of bed.....					

Since the last assessment has the subject been able to return to day care/school, or resume their normal daily activity in the same way as performed prior to developing the flu?  Yes  No

This form was filled out by:

- Parent
- Carer
- Other

Note: The term "Carer" in this questionnaire corresponds to the term "caregiver" used throughout the protocol.

**Baloxavir Marboxil—F. Hoffmann-La Roche Ltd**  
**Statistical Analysis Plan CP40563**

## **STATISTICAL ANALYSIS PLAN AMENDMENT RATIONALE**

This Statistical Analysis Plan (SAP) has been amended to incorporate the following changes:

- Addition of Sparse Pharmacokinetic-Evaluable Population (Section 4.1.6) and Extensive Pharmacokinetic-Evaluable Population (Section 4.1.7).
- Clarification of the baseline definition for Body Temperature (Section 4.5.5).
- Addition of rule for imputation of CARIFS assessment time if the time was not recorded in the correct assessment time period (Section 4.6).
- Clarification of censoring rule in time to event analysis (Section 4.6).
- Clarification on handling rule for missing data in CARIFS assessments.
- Further details on exploratory analysis endpoint Polymorphic and treatment-emergent amino acid substitutions in the PA, PB1, and PB2 genes (Section 4.6.3)
- Addition of subgroups analysis of some secondary endpoints, based on virus type and subtype (Section 4.6.4).
- Additional minor changes have been made to improve clarity and consistency.

## **1. BACKGROUND**

This Statistical Analysis Plan (SAP) provides details of the planned analyses and statistical methods for the clinical efficacy, clinical safety, pharmacokinetic (PK), and pharmacodynamic (PD) data for Study CP40563.

Baloxavir marboxil (also referred to as S-033188, Shionogi Compound Identification Number) is a pro-drug that is converted to an active form (baloxavir, S-033447) in the blood, liver, and small intestine through a metabolic process called hydrolysis.

Baloxavir marboxil acts on cap-dependent endonuclease, an enzyme specific to influenza viruses, and inhibits viral cap-snatching, thereby suppressing the replication of influenza viruses.

## **2. STUDY DESIGN**

This is a multicenter, randomized, double-blind, active-controlled (i.e., oseltamivir) study to assess the safety, PK, and efficacy of baloxavir marboxil compared with oseltamivir in pediatric patients 1 to < 12 years of age with influenza-like symptoms. This study is designed to enroll approximately 120 otherwise healthy male and female pediatric patients with influenza-like symptoms presenting within 48 hours of symptoms onset.

### **2.1 PROTOCOL SYNOPSIS**

The Protocol Synopsis is in [Appendix 1](#) and includes the study objectives, inclusion and exclusion criteria, outcome measures, and statistical methods as stated in the Protocol.

### **2.2 OUTCOME MEASURES**

All assessments and procedures are detailed in the Protocol.

#### **2.2.1 Safety (Primary) Endpoints**

Incidence, severity, and timing of:

- Adverse events (AEs)
- Serious adverse events (SAEs)
- Vital sign measurements
- Clinical laboratory test results

#### **2.2.2 Pharmacokinetic Endpoints**

- Plasma concentrations of baloxavir marboxil (pro-drug) and S-033447 (active metabolite)
- Population PK model derived parameters (e.g.,  $AUC_{inf}$ ,  $C_{max}$ ,  $T_{max}$ ,  $t_{1/2}$ ) (modelling report)

### **2.2.3 Efficacy (Secondary) Endpoints**

- Time to alleviation of influenza signs and symptoms, defined as the length of time taken from the start of treatment to the point at which all of the following criteria are met and remain so for at least 21.5 hours:
  - A score of 0 (no problem) or 1 (minor problem) for cough and nasal symptoms (items 14 and 15 of the Canadian Acute Respiratory Illness and Flu Scale (CARIFS) questionnaire ([Appendix 4](#) )
  - A “yes” response to the following question on the CARIFS: “Since the last assessment has the subject been able to return to day care/school, or resume his or her normal daily activity in the same way as performed prior to developing the flu?”
  - First return to afebrile state (tympanic temperature  $\leq 37.2^{\circ}\text{C}$ )
- Duration of fever (time to return to afebrile state [tympanic temperature  $\leq 37.2^{\circ}\text{C}$ ] and remaining so for at least 21.5 hours)
- Duration of symptoms (alleviation of all symptoms as defined by a score of 0 [no problem] or 1 [minor problem] and remaining so for at least 21.5 hours, for all 18 symptoms specified in the CARIFS questionnaire)
- Time to return to normal health and activity
- Frequency of influenza-related complications (death, hospitalization, radiologically confirmed pneumonia, bronchitis, sinusitis, otitis media, febrile seizures, encephalitis/encephalopathy, myositis)
- Proportion of patients requiring antibiotics

### **2.2.4 Virology (Secondary) Endpoints**

- Time to cessation of viral shedding by virus titer and by reverse transcriptase-polymerase chain reaction (RT-PCR)
- Change from baseline in influenza virus titer and in the amount of virus RNA (RT-PCR) at each time point
- Proportion of patients with positive influenza virus titer and proportion of patients positive by RT-PCR at each time point
- Area under the curve in virus titer and in the amount of virus RNA (RT-PCR)

### **2.2.5 Exploratory Endpoints**

- Polymorphic and treatment-emergent amino acid substitutions in the PA, PB1, and PB2 genes
- Drug susceptibility in patients with evaluable virus
- Non-compartmental PK parameters (intensive PK)

## **2.3 DETERMINATION OF SAMPLE SIZE**

No formal sample-size calculations have been performed. Approximately 120 pediatric patients (80 patients in the baloxavir marboxil treatment group and 40 patients in the oseltamivir treatment group) will be enrolled.

To detect adverse events with a 3% incidence for at least 1 patient with a probability of  $\geq 90\%$ , the study will require 80 patients exposed to baloxavir marboxil. The given sample size provides a probability of at least 1 patient experiencing an adverse event with a true incidence rate of from 1% to 5% as shown in [Table 1](#).

**Table 1 Probability of Adverse Events by Incidence Rates**

	True incidence rate of an AE				
	1%	2%	3%	4%	5
Probability of at least one patient experiencing an AE	55.2%	80.1%	91.3%	96.2%	98.3%

AE= adverse event.

The number of patients in the intention to treat influenza infected (ITTi) population will be monitored on an ongoing basis in order to ensure that an adequate number of influenza-infected patients are recruited. Additional patients may be recruited if the ITTi population is considerably smaller than expected.

## 2.4 ANALYSIS TIMING

The primary study analysis will occur when the last patient has either withdrawn or completed his or her Day 29 visit, and will be based on all available data for all patients up to and inclusive of their Day 29 assessment date, as well as safety follow-up data for patients that withdrew prior to Day 29.

## 3. STUDY CONDUCT

### 3.1 RANDOMIZATION

Following completion of the screening period and after all patient eligibility requirements are confirmed, patients will be assigned a patient number (a different number from the screening number) on Day 1 and will undergo randomization in a 2:1 ratio to baloxavir marboxil or oseltamivir respectively. All patients will receive one of two active treatments: a single oral dose of baloxavir marboxil based on body weight (2 mg/kg for patients weighing  $< 20$  kg or 40 mg for patients weighing  $\geq 20$  kg) or oseltamivir (dose based on body weight) for 5 days. Both groups will receive matching placebo for the alternate treatment. A permuted block randomization method will be used to obtain an approximate 2:1 ratio of baloxavir marboxil to oseltamivir.

### 3.2 DATA MONITORING

To facilitate early and close monitoring of safety parameters over time, an Internal Monitoring Committee (IMC) will review aggregate safety data on an ongoing basis as defined in the IMC [charter](#) and according to the process defined in the Blinding/Unblinding Process document. If there is any concern noted in the safety

parameters, the Sponsor may suspend or discontinue a treatment arm or the entire study, as appropriate.

#### **4. STATISTICAL METHODS**

##### **4.1 ANALYSIS POPULATIONS**

Disposition summaries will be based on the Randomized Population. Analysis of safety data will be based on the safety population. The primary analysis population for efficacy will be the ITTi population.

###### **4.1.1 Randomized Population**

The randomized population will include all patients randomized in the study.

###### **4.1.2 Per Protocol Population**

Not applicable.

###### **4.1.3 Intent-to-Treat Population**

The intent-to-treat (ITT) population comprises all patients who received at least one dose of treatment regardless of whether they have any follow-up assessments. Patients will be grouped on the basis of randomized treatment. If there is any doubt whether a patient was treated, that patient will be assumed to have been treated for the purpose of analysis.

###### **4.1.4 Intent-to-Treat Influenza-Infected Population**

The ITTi population is a subset of ITT patients who have had a laboratory confirmation of influenza infection (polymerase chain reaction [PCR] result) from any swab sample collected at baseline or during the study. The ITTi population is the primary efficacy population, unless specified otherwise. Patients will be grouped based on randomized treatment.

Decisions on patient exclusion from the ITTi population will be made prior to database closure. Excluded patients will be documented, together with the reason for exclusion.

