#### **4.1.1 Inclusion Criteria**

Patients must meet the following criteria for study entry:

- Written informed consent/assent for study participation obtained from patient's parents or legal guardian, with assent as appropriate by the patient, depending on the patient's level of understanding
- Aged 1 to <12 years at randomization (Day 1)
- Parent/guardian willing and able to comply with study requirements, in the investigator's judgment
- Patient able to comply with study requirements, depending on the patient's level of understanding
- Patient with a diagnosis of influenza virus infection confirmed by the presence of all of the following:
  - Fever  $\geq 38^{\circ}\text{C}$  (tympanic temperature) at screening
  - At least one respiratory symptom (either cough or nasal congestion)

- The time interval between the onset of symptoms and screening is  $\leq 48$  hours (the onset of symptoms is defined as the time when body temperature first exceeded 37.5°C if known, or the time when the first symptom was noticed by patient, parent, or caregiver)

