## Appendix 1 Schedule of Activities

Day(s)	Treatment Period						Follow-Up Period				
	D1		D2	D3	D4	D5	D6	D7-9	D10	D15	D29 or ET
Visits	V1 Screening	V1 Post-dose	V2	OpV1 a	V3		V4		V5	OpV2 a	V6
Visit Window (days)					+1		±1		±2	±3	±3
Written informed consent/assent	x										
Inclusion/exclusion criteria	x										
Demographics	x										
Medical history b	x										
Randomization	x										
Study drug administration c		x	x	x	x	x					
Patient diary:											
Body temperature measurement d	Four times daily				Twice daily			Once daily			
Assessment of influenza symptoms e	Twice daily							Once daily			
Physical examination	x f		x f	(x) f	x f		x		x	(x g )	x f
Vital signs measurement	x		x	(x)	x		x		x	(x g )	x h
Adverse event assessment		x	x	(x)	x		x		x	(x g )	x
Concomitant therapies assessment	x		x	(x)	x		x		x	(x g )	x
Interview for meal consumption	x	x									
Clinical laboratory tests		x					x			(x g )	(x g )
Nasal/nasopharyngeal swabs (virology test) i	x		x		x		x		x	(x g )	(x g )

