## Appendix 1 Schedule of Activities (cont.)

Day(s)	Treatment Period					Follow-Up Period					
	D1	D2	D3	D4	D5	D6	D7-9	D10	D15	D29 or ET	
Visits	V1 Screening	V1 Post-dose	V2	OpV1 a	V3		V4		V5	OpV2 a	V6
Sparse PK samples j		x	(x) j		(x) j		x j				
Intensive PK samples k		x	x		x		x k				

CARIFS= Canadian Acute Respiratory Illness and Flu Scale; D=Day; ET=early termination; OpV=optional visit; PK=pharmacokinetic; V=visit.

- a OpV1 and OpV2 are optional visits to be performed at the discretion of the investigator or parent/caregiver, for example, to obtain intensive PK analyses, or in the event of persistent influenza symptoms.
- b Prior therapies will also be reviewed.
- c Oseltamivir and matching placebo will be given orally, 12 hours apart. If the first dose is taken after 4 pm (16:00 hours) on Day 1, the next dose will be taken in the morning of Day 2. For these patients, the 10th dose will be taken on the morning of study Day 6. If the first dose is taken prior to 4 pm (16:00 hours) on Day 1, the next dose should be taken in the evening of the same day (i.e., prior to midnight on the same calendar day with a minimum of 7 hours between doses). For these patients, the 10th dose will be taken in the evening of study Day 5.
- d The parent/caregiver will assess and record in the patient diary, body temperature (tympanic assessment) four times daily (morning, noon, evening, and bedtime) from Days 1 to 3; twice daily (morning and evening) on Days 4 to 9; once daily on Days 10 to 15.
- e The parent/caregiver will complete the CARIFS questionnaire twice daily (morning and evening) on Days 1 to 9 and then once daily on Days 10 to 15.
- f Body weight and height will be measured on Days 1 and 29, only. Physical examinations on Days 2, 3, and 4 will be limited symptom-directed physical examinations and may be performed by a mobile nursing professional.
- g Conduct assessment if the investigator determines that influenza symptoms or viral shedding are persisting or at the investigator's discretion.
- h Vital signs will be recorded if abnormal physical examination findings or adverse events are recorded since last visit or at investigator's discretion on Day 29.
- i At least two nasal and/or nasopharyngeal swabs (one for each nostril) to be taken at each visit.

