#### **4.6 EFFICACY ANALYSIS**

The statistical analyses of efficacy endpoints will be descriptive. The ITTi population will be used for all analyses. Additional analysis of efficacy analysis presenting the ITT population will not be completed.

The data will be summarized using means, standard deviations, medians, and ranges for continuous variables and proportions for categorical variables, as appropriate. Time-to-event endpoints and duration endpoints will be summarized using Kaplan-Meier plots and summaries of the median survival time. Summaries will be presented by treatment group.

Efficacy endpoints are based on the CARIFS questionnaire data which is recorded by parent/ caregiver using handheld device. This assessment data should be recorded for the following time periods:

Period	Time
Morning	0.500-10.59
Noon	11.00-14.59
Evening	15.00-18.59
Bedtime	19.00-23.59

\*data should not be recorded between 00.00 and 4.59.

In the case where the recorded time of an assessment is outside the period time window for that assessment, the end time of the period should be imputed as the assessment time.

In the case where the assessment time falls into the period between 00.00 and 4.59 (due to technical error) the assessment date will be imputed to the date prior to recorded assessment date and the assessment time will be imputed to the end time of the period time window.

The imputation method used in the derivation of time to alleviation of influenza signs and symptoms is described in Section 4.6.1. No further imputation methods will be used.

In all time to event analysis, patients who withdraw prior to event of interest will be censored at the last observation timepoint.

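### For children without a positive Day 1 PCR, entry to the efficacy population depends on viral detection after dosing, and no clinical efficacy summary is planned in a set fixed before dosing.

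*SAP*

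**What the plan says.** **Population.** SAP 4.1.4 and Protocol 6.1.4 use the same rule: a treated child belongs to ITTi if PCR confirms influenza "from any swab sample collected at baseline or during the study". Neither sets a cut-off day. SAP 4.1.4 adds: "The ITTi population is the primary efficacy population, unless specified otherwise".

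**Study entry.** Protocol 4.1.1 asks for a "Patient with a diagnosis of influenza virus infection confirmed by the presence of all of the following", and what follows is fever, a respiratory symptom and onset within 48 hours. No virological test is required, so children who are PCR-negative at baseline can be randomised.

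**Swabs.** In Protocol Appendix 1 the Day 1 swab is taken at screening, before dosing. Swabs are mandatory again on Days 2, 4, 6 and 10. Those on Day 15 and on Day 29 or early termination are conditional, under footnote g: "Conduct assessment if the investigator determines that influenza symptoms or viral shedding are persisting or at the investigator's discretion".

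**Analysis sets.** Protocol 6.7 planned ITTi for all efficacy analyses, with ITT described as well for the main one. SAP 4.6 keeps ITTi and says the ITT presentation will not be done. SAP 4.6.2 restricts the titer endpoints to children with a positive Day 1 titer and the RNA endpoints to children with positive Day 1 RNA. SAP 4.6.1 has no such restriction for the clinical endpoints. SAP 4.6 also states: "The statistical analyses of efficacy endpoints will be descriptive".

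**The concern.** Membership of an efficacy population should be fixed by information from before treatment. For a child with a positive Day 1 PCR it is. For a child whose Day 1 PCR is negative or missing, membership is decided by whether virus is detected after dosing. The trial compares the arms on exactly that, as a secondary virology objective. If one drug clears virus faster, fewer such children enter in that arm, and those who do enter are selected for slow clearance.

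A second route has nothing to do with clearance. A child enrolled with another illness who catches influenza during follow-up also enters. Time to alleviation for that child still runs from the Day 1 dose, and the symptom diary stops at Day 15, so the recorded time may describe the other illness.

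At stake are time to alleviation, duration of fever, duration of symptoms, return to normal activity, complications and antibiotic use. With the ITT summary dropped, none of these is planned in any set that post-dose detection cannot alter.

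**Working it through.** **1. The plan's own figures.** Neither document states an expected ITTi size or a baseline-negative share. The only sample-size figures are the adverse-event probabilities in SAP Table 1. With 80 baloxavir patients, 1 − (1 − p)^80 gives 55.25%, 80.14%, 91.26%, 96.18% and 98.35% for p = 1% to 5%. These agree with the table and confirm the arm size, but say nothing about ITTi.

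**2. Which swab can decide membership.**

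| First positive PCR | Who is swabbed | Is membership fixed before dosing? |
|---|---|---|
| Day 1, pre-dose | everyone | yes |
| Day 2, 4, 6 or 10 | everyone | no |
| Day 15 or Day 29/ET | conditional (footnote g) | no; needs no positive on Days 1, 2, 4, 6 and 10 |

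The mandatory post-dose swabs are therefore the main route. The conditional ones matter only after five negative or missed swabs.

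**3. How many children.** Inputs from the documents: "80 patients in the baloxavir marboxil treatment group and 40 patients in the oseltamivir treatment group" (SAP 2.3), and median cessation of shedding by titer of 24 h on baloxavir and 72 h on oseltamivir in the adult and adolescent trial (Protocol 1.2.2). Assumptions: all 120 children are infected; a share s in each arm is missed at baseline; a missed child is found only if still shedding at 24 h; shedding time is exponential.

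- Probability found: baloxavir 2^(−24/24) = 0.50; oseltamivir 2^(−24/72) = 0.794.
- Late entrants: 80 × s × 0.50 and 40 × s × 0.794.
- Arm imbalance, meaning the baloxavir children who would also have entered at the oseltamivir rate: 80 × s × (0.794 − 0.50).

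| s | Day 1 positives | ITTi, any swab | Late entrants | Late share of arm | Imbalance |
|---|---|---|---|---|---|
| 2% | 78.4 / 39.2 | 79.2 / 39.8 | 0.8 / 0.6 | 1.0% / 1.6% | 0.5 |
| 5% | 76 / 38 | 78.0 / 39.6 | 2.0 / 1.6 | 2.6% / 4.0% | 1.2 |
| 10% | 72 / 36 | 76.0 / 39.2 | 4.0 / 3.2 | 5.3% / 8.1% | 2.3 |

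(baloxavir / oseltamivir)

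A milder set of assumptions is 96 infected children (64 and 32), 5% missed (3.2 and 1.6), and later positivity of 50% and 70%. Then 1.6 and 1.1 children enter late, and the imbalance is 3.2 × 0.20 = 0.64 child.

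**4. Effect on the median, extreme case.** Give both arms the same true median, 53.7 h (the baloxavir figure in Protocol 1.2.2, for a different symptom endpoint). Let every late entrant have a very long illness. With late share f the observed median solves (1 − f)S(t) + f = 0.5. For a Weibull S with shape k, t = 53.7 × {−ln[(0.5 − f)/(1 − f)] / ln 2}^(1/k).

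| s | Baloxavir, k = 1.5 to 1 | Oseltamivir, k = 1.5 to 1 | Spurious gap |
|---|---|---|---|
| 2% | 54.2 to 54.5 h | 54.5 to 55.0 h | 0.3 to 0.5 h |
| 5% | 55.1 to 55.8 h | 55.9 to 57.0 h | 0.8 to 1.2 h |
| 10% | 56.6 to 58.1 h | 58.4 to 60.9 h | 1.8 to 2.7 h |

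Here the gap favours baloxavir, because every late entrant is given the same long illness and proportionally more of them enter on oseltamivir. In practice the baloxavir entrants would be the more strongly selected for slow clearance (the slowest 50%, against the slowest 79%), which pulls the other way. The direction is not established.

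**The case against.** **The assay differs.** ITTi entry is by PCR, while the 24 h and 72 h medians are for titer. In the Japanese paediatric study (Protocol 1.2.3) the Day 2 mean change was −4.20 log10 in titer but only −1.75 log10 in RNA. PCR may therefore stay positive longer in both arms and narrow the difference. This stands. It does not exclude a difference, since that study reports no PCR-positivity rate, but it makes the figures above more likely too large than too small.

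**The rule has a purpose.** Any-swab confirmation keeps infected children whose baseline swab was falsely negative, missing or unusable, in a trial of about 120. It is objective, pre-specified and the same in both documents. This stands, and is why replacing the rule with Day 1 PCR would be a debatable trade-off. Nor could such a replacement be justified as the rule all virology endpoints already follow: the titer endpoints require a positive Day 1 titer, and only the RNA endpoints require positive Day 1 RNA.

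**The conditional swabs.** A reader might infer that Day 15 and Day 29 swabs, taken because a child is still ill, drive entry. The documents do not support this. Those swabs decide membership only when no swab on Days 1 to 10 was positive, footnote g also allows them at the investigator's discretion, and site staff are blinded (Protocol 4.2.1). A first positive that late looks more like a new infection than slow clearance.

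**Conclusion.** The point holds as a small gap in the efficacy plan. For children with a negative or missing Day 1 PCR, ITTi membership can depend on treatment or on a later infection, and no planned summary of the clinical endpoints is free of this.

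The size is unknown, because the documents give no baseline-negative share. For assumed shares of 2% to 10%, about 1.4 to 7.2 children enter late in the two arms together. The arm imbalance is about 0.5 to 2.3 children, and at most 2.7 h on the median in a deliberately extreme case. These figures rest on adult and adolescent titer data, exponential shedding and full infection of the sample.

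A reader might infer that the randomised comparison is broken. That goes too far. Baseline-positive children are in ITTi whatever happens later, the virology endpoints carry their own Day 1 restriction, and the primary safety analysis uses the safety population. Efficacy is secondary and descriptive with no hypothesis test, so type I error is not at issue; the risk is a slightly biased contrast between arms.

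**What to change.** In SAP 4.1.4 and 4.6:

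1. Keep the any-swab ITTi as defined.
2. Also report time to alleviation and the other clinical efficacy endpoints in children who are PCR-positive on the pre-dose Day 1 swab.
3. List by arm the children who entered ITTi only on a post-dose swab, with the day of first positive PCR and whether the Day 1 result was negative or missing.

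If the list is empty, the two sets coincide and the question closes. The swab is already collected, so the cost is SAP wording and a few extra tables. The added set is slightly smaller, because it omits infected children with a false-negative or missing baseline swab. Those children remain in ITTi.
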